**The Effect of Etelcalcetide on Bone-tissue Properties and Calcification
Propensity in End Stage Kidney Disease**

Principal Investigator: [name], MS

AAAR6244

NCT03960437

Protocol Version January 3, 2020

Title: The effect of etelcalcetide on bone-tissue properties and calcification propensity in end stage kidney disease

Hypotheses: Our hypothesis is that etelcalcetide treatment improves bone tissue-properties and bone mineral density by reducing remodeling. We also hypothesize that etelcalcetide's ability to lower serum calcium will decrease propensity of serum to calcify as determined by T50.

[figure not shown]
Background and Study Objectives

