Chronic kidney disease – mineral and bone disease (CKD-MBD) is a systemic disorder of bone and mineral metabolism in patients with CKD. As kidney function declines, abnormal vitamin D metabolism and renal phosphate handling drive the development of hyperparathyroidism (HPT), hyperphosphatemia, renal osteodystrophy and soft tissue calcifications. Clinical outcomes associated with CKD-MBD include bone fractures, cardiovascular events and death. Treatment of CKD-MBD is centered around the suppression of parathyroid hormone (PTH) by supplementation with vitamin D (parent and active D) and correction of hyperphosphatemia. In patients with end stage kidney disease (ESKD), target levels of PTH recommended by the Kidney Disease Improving Global Outcomes (KDIGO) guidelines are in the range of 2-9 times the upper limit of normal (ULN) for the PTH assay¹. However, in patients with long-standing ESKD, abnormalities may develop in the parathyroid gland that both diminish responsiveness to treatment and lead to failure to achieve PTH levels within the KDIGO target range. PTH levels greater than the target range increase the risks of bone loss, fractures, soft tissue calcification and cardiovascular events. In these cases, treatment with a calcimimetic, a pharmacologic agent that enhances sensitivity of the parathyroid gland to serum levels of calcium, can restore PTH levels to goal. Etelcalcetide is a Food and Drug Administration (FDA) approved calcimimetic for the treatment of secondary HPT in adult patients with CKD on hemodialysis²⁻⁴. The proposed prospective cohort study will investigate the effects of etelcalcetide on the bone and vascular calcification components of CKD-MBD. We will test if treatment with etelcalcetide improves bone properties on the tissue level, increases areal bone mineral density (BMD) by dual energy X-ray absorptiometry (DXA), improves cortical and trabecular BMD and microarchitecture and mechanical competence by high resolution peripheral computed tomography (HR-pQCT), and decreases serum propensity to calcify soft tissues. For all Aims, the enrollment scheme and study timeline are described in Figures 1 and 2, respectively.

Hypothesis 1. Etelcalcetide improves bone-tissue properties in patients with ESKD and severe hyperparathyroidism.

Aim 1. To test if 6-months of treatment

Figure 1. Study Procedures for All Aims

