HR-pQCT Finite Element Analysis (FEA). [name] will estimate mechanical competence (strength) from HR-pQCT images. Each image is converted to a μ FE model by directly converting bone voxels to 8-node elastic brick elements. A uniaxial displacement equaling 1% of the bone segment height is applied perpendicularly to the distal surface of the radius or tibia while the proximal surface is imposed with zero displacement along the same direction. The total reaction force is calculated from the linear μ FE analysis, and the axial stiffness is calculated as the reaction force divided by the imposed displacement.

HR-pQCT Cortical Porosity. [name] will conduct analyses of cortical porosity using methods that have been described and validated in recent publications⁸.

Hypothesis 3. Etelcalcetide decreases serum calcification propensity in patients with ESKD.

Aim 3. To test if 6-months of treatment with etelcalcetide decreases serum propensity to calcify soft tissues. In a single-arm study of 35 patients with ESKD treated with 6-months of etelcalcetide, we will measure T50, calcitropic hormones, serum calcium and phosphorus, bone turnover markers, FGF-23 and Sclerostin pre-treatment and 3- and 6-months after treatment.

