Sample Size Justification for Aim 2. The proposed sample size of 35 participants provides >80% power and 5% alpha to detect a change in femoral neck BMD of 0.5% f and a 0.5 standard deviation change in radius failure load by HR-pQCT from pre-treatment to the 6-month endpoint. For femoral neck BMD by measured by DXA, Lien et al¹⁵ reported that in 8 patients with CKD treated with cinacalcet for 6 months, areal BMD at the femoral neck increased $2.2 \pm 1.1\%$ ($p < 0.05$). For failure load outcomes, in a longitudinal study of 29 patients with ESKD who underwent kidney transplantation, we reported that failure load decreased by $3.5 \pm 7.0\%$ ($p=0.0081$) over 12-months¹⁶; our larger sample size will permit detection of at least a 3.4% change in radius failure load due to suppression of PTH production by etelcalcetide.

Sample Size for Aim 3: N = 35 (20 from Aim 1 plus 15 additional patients)

Sample Size Justification for Aim 3: The proposed sample size of 35 participants provides >80% power and 5% alpha two-tailed dependent T-test of the change in T50 from baseline to the 6-month endpoint. Based on Smith et al¹⁰, each standard deviation (SD) decrease in T50 was associated with a 39% increase in odds of all-cause mortality. Assuming that the variability in T50 in patients on hemodialysis patients enrolled into this prospective cohort study are similar to those reported in Smith et al¹⁰, approximately 20 patients would be required to detect a 1-SD decrease in T50. Our sample size of 35 patients will permit the detection of a 0.7-SDs decline in T50. We assume that a reduction of lesser magnitude is of unclear clinical significance

Protection of Human Subjects

This study qualifies as clinical research and will be conducted in compliance with GCP and all regulatory requirements for the protection of human subjects.

Informed Consent

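### Does it matter that the Aim 3 sample-size rationale words the detectable T50 effect as a fall, when Hypothesis 3 seeks lower calcification propensity?

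*Combined protocol and SAP*

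**What the plan says.** The opening hypothesis statement says that etelcalcetide "will decrease propensity of serum to calcify as determined by T50". Hypothesis 3 repeats the claim: "Etelcalcetide decreases serum calcification propensity in patients with ESKD". The Aim 3 primary endpoint, under Primary and Secondary Endpoints for Each Aim, is the change in T50, percent and absolute, with no sign attached. The statistical methods for Aim 3 specify a two-tailed paired t-test from baseline to the 6-month endpoint.

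The Sample Size Justification for Aim 3 opens in the same neutral way, with a "two-tailed dependent T-test of the change in T50 from baseline to the 6-month endpoint". It then cites a cohort study in which each SD "decrease in T50 was associated with a 39% increase in odds of all-cause mortality". From there it speaks only of falls: "approximately 20 patients would be required to detect a 1-SD decrease in T50", then "Our sample size of 35 patients will permit the detection of a 0.7-SDs decline in T50", and finally "We assume that a reduction of lesser magnitude is of unclear clinical significance".

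**The concern.** Within one paragraph, a lower T50 is the marker of higher mortality and is also the change the study is said to be able to detect. Hypothesis 3 is about benefit. If a low T50 reflects a high tendency to calcify, the hypothesis predicts a rise, and the paragraph describes the opposite.

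T50 is the only primary endpoint of Aim 3, and these phrases are the only place where a detectable change in T50 is given a sign. A reader could conclude that the trial was sized for harm, or that a fall would count as success. The closing remark on clinical significance is also tied to the unfavourable direction. If any decision rule, one-sided test or responder threshold took its sign from this paragraph, the primary conclusion of Aim 3 could be read backwards.

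**Working it through.** **1. Which direction is favourable?**

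- Hypothesis 3: propensity to calcify should fall.
- Sample Size Justification for Aim 3: lower T50 goes with higher odds of death.
- Reference list: the title of the study cited for that figure says that serum calcification propensity predicts mortality. It does not give the sign.

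Together these make a low T50 the high-propensity state and a rise the hoped-for change. This is a reasonable inference, but no section states that a higher T50 means lower propensity.

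**2. Do the plan's own figures reproduce?**

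Inputs from the Aim 3 sample-size text: N = 35, two-sided alpha 5%, power above 80%, paired t-test, effect 0.7 SD, and about 20 patients for 1 SD. The SD is that of T50 in the cited cohort. No numeric SD and no pre/post correlation r is given, so r is an assumption here.

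Formulas:

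- SD of change = SD × √(2(1 − r))
- standardised effect d = 0.7 SD / SD of change
- noncentrality = d × √35, with 34 degrees of freedom

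| Assumed r | SD of change (in SDs) | d | Noncentrality | Power, 0.7-SD fall | Power, 0.7-SD rise |
|---|---|---|---|---|---|
| 0 | 1.414 | 0.495 | 2.93 | 0.812 | 0.812 |
| 0.5 | 1.000 | 0.700 | 4.14 | 0.980 | 0.980 |

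At r = 0, a 0.7-SD effect needs 35 patients for 80% power, the minimum detectable effect at N = 35 is 0.689 SD, and a 1-SD effect needs 18 patients. These agree with the stated 35 and with the stated figure of about 20. At r = 0.5 the minimum detectable effect is 0.487 SD, so the stated figures sit at the cautious end of this range.

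**3. Does the sign enter the calculation?**

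The two-sided test rejects when |t| exceeds the critical value. Replacing d by −d swaps the two tails and leaves their sum unchanged, as the last two columns show. The required N is likewise the same for a rise.

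**4. Does anything downstream use the sign?**

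| Element | Carries a direction for T50? |
|---|---|
| Aim 3 primary endpoint | No, a change |
| Primary test | No, two-tailed |
| Mixed model over 0, 3 and 6 months | No, time effect |
| Regressions of T50 change on other markers | No |
| Success criterion or threshold at 0.7 SD | None exists |
| Remark on smaller reductions | Yes, but no analysis refers to it |

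The estimate is reported with whatever sign the data give it, and nothing in the analysis reads the sizing paragraph to interpret it.

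**The case for a change.** The best argument for a change is that neither assay direction makes the paragraph fit well. If a lower T50 means higher propensity, the change described runs against Hypothesis 3. If a lower T50 means lower propensity, the change fits the hypothesis, but the mortality sentence then ties success to more deaths, which undercuts its use as the clinical rationale. The authors also write neutrally elsewhere, so the fall wording is not simply their habit. The statistical methods put T50 in brackets after calcification propensity, as though the two moved together, which could mislead a newcomer. The correction would cost a few words.

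Part of this stands: the wording is loose, and the protocol does not say which direction of T50 is good. It falls short of a contradiction. The sentence is about what can be detected, and it is true as written. Nowhere does the paragraph call a fall expected, sought or beneficial. The likeliest explanation is that the authors took their unit from the cited association, which is expressed per SD decrease, and stayed on that scale for the next three statements. A reader who took a fall for success would also have to overlook the mortality sentence in the same paragraph. Low cost alone is not a reason to amend when the amendment alters nothing that is done or concluded.

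**Conclusion.** The observation is accurate as a comment on wording, but it needs no change to the plan. The numerical effect is nil: N stays at 35, power at 0.7 SD is the same for a rise and a fall (0.812 at r = 0 and 0.980 at r = 0.5), and the test, estimate and p-value are untouched. The endpoint and test have no direction, and no success rule draws on the 0.7-SD figure or the remark that follows it, so following the document as written leads to the same result and the same conclusion.

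The power values assume the between-patient SD applies equally at both visits, with r between 0 and 0.5. The equality of power for the two signs needs neither assumption; it follows from the two-sided test. That a rise is the favourable direction is inferred from the mortality sentence and Hypothesis 3. The conclusion does not depend on that inference, because the analysis is the same either way.

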We will enroll 20 adult patients with ESKD on hemodialysis who are scheduled to receive etelcalcetide for the treatment of HPT per standard of care. These 20 patients with ESKD will be treated with etelcalcetide to maintain levels of PTH between 300 and 400 pg/mL, which is at the mid-range of the KDIGO recommended range (2-9 times the ULN for the PTH assay¹) for 6 months. Patients will be identified for inclusion based on clinical need for the treatment of severe HPT and high turnover bone disease and only patients whose treating physician plans to initiate etelcalcetide will be included. HPT will be defined by the KDIGO guidelines (PTH >9-times the ULN for the PTH assay¹) and high turnover bone disease will be defined by a total alkaline phosphatase level \geq upper tertile of the reference range for the assay. At study start, patients will undergo the initial double labeling procedure with tetracycline (TCN; 3-days of TCN followed by 12-days off TCN followed by 3-days of TCN); during the labeling period etelcalcetide will not be administered (**Figure 2**). Patients will then undergo a 3-month etelcalcetide dose-titration phase to ensure that PTH levels are consistently maintained within target range (300-400 pg/mL), followed by a 6-month treatment (maintenance) phase. At the study endpoint (6-months of treatment), the final set of labels for transiliac crest bone biopsy will be given (3-days of demeclocycline followed by 12-days off demeclocycline followed by 3-days of demeclocycline) and bone biopsy will occur 5-days after the last dose of demeclocycline. During the final labeling period, the dose of etelcalcetide will continue to target the goal PTH level and the patient will continue to be managed as clinically indicated. The quadruple label approach permits longitudinal assessment of both dynamic indices of histomorphometry and bone-tissue level properties pre- and post-intervention, with the use of a single biopsy. The first label (TCN) is given prior to the initiation of etelcalcetide and the second label (demeclocycline) is given after 6-months of treatment (maintenance) with etelcalcetide. The fluorescence of tetracycline and demeclocycline differs, permitting differentiation of the labels under fluorescence microscopy and determination of dynamic indices of histomorphometry pre- and post-intervention. To assess bone tissue level effects of treatment, we will use a Raman/Nanoindentation system. This system allows the differentiation of tetracycline (pre-treatment) and demeclocycline (post-treatment) labels and permits precise measurement of localized bone tissue properties (e.g., mineral/matrix, collagen) and indentation properties (e.g., hardness) within these regions. Additionally, we will use 3-dimensional micro-CT (μ CT) imaging (resolution 3 μm^3) to obtain more complete structural indices from the bone biopsy specimens at the 6-month time point. Patients will have blood collected and stored at -80°C, at baseline (pre-treatment) and after 3- and 6-months of treatment (i.e., maintenance phase) (**Table 1**). Blood will be assayed for calcium, phosphorus, PTH, vitamin D metabolites, bone formation (bone specific alkaline phosphatase [BSAP], procollagen type-1 N-terminal propeptide [P1NP]) and resorption (C-Telopeptide [CTX]) markers, FGF-23 and sclerostin.

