Procedures. We will enroll 35 patients (20 from Aim 1 and 15 *de novo*) into this prospective single-arm cohort study to test the hypothesis that 6 months of treatment (maintenance) with etelcalcetide will decrease the propensity to calcify soft tissues as measured by T50. Similar to **Aim 1**, eligibility for enrollment into **Aim 3** will be based on a PTH level >9-times the ULN for the PTH assay (**Figure 1**), as well as their treating physician's plan to initiate etelcalcetide per standard of care. However, the presence of high turnover bone disease based on total alkaline phosphatase will not be a criterion for enrollment into **Aim 3**. Furthermore, all patients enrolled in **Aim 1** will be automatically enrolled into **Aim 3** unless they choose to opt-out of **Aim 3**. Thus, we will use the biochemical data from the 20 enrollees participating in **Aim 1** and enroll an additional 15 patients to be treated with etelcalcetide. As per **Aim 1** (**Figure 2**), after enrollment, patients will undergo a 3-month dose titration phase to ensure that PTH levels are stability maintained within the target range (300-400 pg/mL), followed by a 6-month treatment (maintenance) phase. Patients will have blood collected and stored at -80°C, at baseline (pre-treatment) and after 3- and 6-months of treatment (i.e., maintenance phase). Blood will be assayed for T50, calcium, phosphorus, PTH, vitamin D metabolites, bone formation (BSAP, P1NP) and resorption (CTX) markers, FGF-23 and sclerostin. We will assess the effect of treatment on changes in levels of T50, a clinically relevant biomarker of calcification propensity^{9, 10}. We will also determine relationships between changes in T50 and changes in phosphorus, calcium, bone turnover markers and calcitropic hormones.

Exploratory. None

Primary and Secondary Endpoints for Each Aim

Aim 1

1. Primary Endpoints: Hardness
2. Secondary Endpoints: Bone formation rate, mineralization density

Aim 2

1. Primary Endpoints: Changes in: (a) femoral neck areal BMD by DXA and (b) radius failure load by HR-pQCT
2. Secondary Endpoints: Changes in: (a) spine, total hip, and one-third and ultradistal radius BMD by DXA and (b) radius and tibia cortical density, thickness, porosity and tissue mineral density, and trabecular density, thickness, number and spacing

Aim 3

1. Primary Endpoint: Change in T50 (percent and absolute)
2. Secondary Endpoints: Changes in PTH, calcitropic hormones, FGF-23, Sclerostin, calcium and phosphorus

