Informed consent will be obtained from all participants. The purpose of the study will be explained to patients prior to recruitment as part of the informed consent procedures, which is defined as “to evaluate the effects of etelcalcetide on bone quality and the tendency of your soft tissue to calcify”. The study methods, namely the assessment of physical exam and medical history; the evaluation by imaging modalities; the collection of blood; and bone biopsy will be described. The fact that the informed consent and the study protocol have been approved by the IRB will be emphasized. The potential risks and direct benefits to the patient will be explained. The potential benefit from this study to future patients will be explained. The fact that the patient has the option not to participate and will receive the same standard medical care regardless of participation will be emphasized. The rights of the patient, including the voluntary nature of participation and the right to withdraw the consent at any time, will be explained. We will also explain that this research does not affect the clinical management of the patient as determined by their nephrologist. In addition, patients will be informed that by enrolling they will have more intensive monitoring of bone health than they would if they do not participate. Thus, participating in this study should not put the subject at any risk for altering management deemed appropriate by the patient's nephrologist. The methods in place for maintaining patient confidentiality will be explained. This will include registering all data under a subject specific alpha-numeric system, storing all records in password protected and encrypted files. A copy of the signed informed consent will be placed in the patient's permanent medical record, a second copy of all consents will accompany the data to be kept in the PI's office, and a third copy will be provided to the participant.

Potential Risks

All key personnel involved in the design or conduct of research involving human subjects will have received the required education on the protection of human research participants prior to funding of this project.

The potential risks are related to hypocalcemia, loss of confidentiality, radiation exposure from DXA for measurement of bone density and HR-pQCT for measurement of volumetric density and microarchitectural parameters and the bone biopsy procedure. All blood will be obtained from the dialysis line to avoid venipuncture.

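### The Informed Consent section says the research does not affect the nephrologist's management, but the protocol sets when etelcalcetide may start in Aim 1 and a PTH target with dosing steps in all aims

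*Combined protocol and SAP*

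**What the plan says.** The Informed Consent section, under Protection of Human Subjects, sets out what patients will be told. On treatment it says: "We will also explain that this research does not affect the clinical management of the patient as determined by their nephrologist". Two sentences later it concludes that "participating in this study should not put the subject at any risk for altering management deemed appropriate" by the nephrologist.

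Elsewhere the protocol specifies parts of that treatment:

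- **Start of drug, Aim 1.** In the Aim 1 Procedures, initial labeling is three days of tetracycline, twelve days off and three days on, and "during the labeling period etelcalcetide will not be administered". The same paragraph adds: "The first label (TCN) is given prior to the initiation of etelcalcetide".
- **PTH target, all aims.** Aim 1 patients "will be treated with etelcalcetide to maintain levels of PTH between 300 and 400 pg/mL". The Aim 2 and Aim 3 Procedures use the same range: "patients will undergo a 3-month dose titration phase to ensure that PTH levels are stability maintained within the target range (300-400 pg/mL").
- **Dosing steps, all aims.** The section on administration and dosing of etelcalcetide gives a starting dose of 5.0 mg, a maximum of 15.0 mg, and increases of 2.5-5.0 mg at weeks 4, 8 and 12 and then at the monthly labs. It also gives rules for low calcium and low PTH.

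Two provisions protect the treating physician's role. Inclusion criterion 12 (all aims) requires that physician to find the protocol's dose and timing suitable for the patient. The last paragraph of Safety Reporting lets the principal investigator make recommendations only.

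**The concern.** The statement to patients is unqualified, while the protocol determines two things a patient would count as management: when a planned drug may first be given, and the PTH level toward which its dose is adjusted. A patient told that management is unaffected would be deciding on an inaccurate premise.

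The design features themselves are not the problem. Aim 1 needs a drug-free label to obtain a pre-treatment value of hardness, its primary endpoint, from a single biopsy. The PTH target defines the treatment whose effect all three aims estimate. Because the design depends on both, the consent plan should state them.

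**Working it through.** The plan gives no figure on this point to reproduce. The check sets the consent statement beside the treatment provisions, with simple arithmetic.

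1. **Is etelcalcetide already part of usual care at entry?** Yes. Inclusion criterion 7 (all aims) requires that the patient is scheduled to receive it as standard of care. The Aim 1 Procedures admit only patients whose physician plans to start it.

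2. **Length of the drug-free labeling period (Aim 1 Procedures).** 3 + 12 + 3 = 18 days. The reason given is to place a label before treatment; no clinical reason is offered. It comes before the first dose, so it postpones a start and does not interrupt treatment. At the final labeling etelcalcetide continues, so no second hold arises.

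3. **Who is affected.** Aim 1 has 20 patients. With 15 further patients for Aims 2 and 3, the total is 20 + 15 = 35. The labeling period applies to the 20; the target and dosing steps apply to all 35.

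4. **The PTH range that the protocol calls controlled.** Inclusion criterion 6 puts 9 times the upper limit of normal at 720 pg/mL for the site's assay, so the upper limit is 720 / 9 = 80 pg/mL. Exclusion criterion 3 calls 2 to 9 times that limit controlled: 2 x 80 = 160 to 9 x 80 = 720 pg/mL.

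5. **The study target on the same scale.** 300 / 80 = 3.75 and 400 / 80 = 5.0 times the upper limit. The target lies inside the controlled range and is narrower than it. A treated patient at 500 pg/mL (500 / 80 = 6.25 times the limit) is controlled by exclusion criterion 3 but above the study target.

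6. **Does the target feed into dosing?** Yes. Under item 4c(2) of the dosing section, after a mild calcium drop has been corrected, the dose goes up by 2.5 mg if PTH is above the target range. Item 4d does the same after a hold and restart, if calcium stays normal and PTH is above goal. I read target range and goal here as 300-400 pg/mL, the meaning given in the aim descriptions.

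7. **Comparison.** Steps 2 and 6 are protocol provisions on drug start and dose. The consent statement says the research has no effect on management. Both cannot be accurate as written.

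**The case against.** The strongest reply is that the sentence is qualified: it speaks of management as the nephrologist determines it. The drug must already be that physician's plan, the physician must accept the dose and timing, and the investigator only advises. On this reading the sentence means that the nephrologist stays in charge. That much stands, and the corrected text should say so. But a physician's agreement to protocol timing and targets does not make the research without effect, and it does not inform the patient.

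A reader might also infer more than the documents support:

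- **That Aim 1 patients lose 18 days of treatment.** No usual-care start date is given, so the delay relative to usual practice is unknown. Entry already requires two consecutive monthly PTH values, and nothing suggests an urgent start.
- **That patients will be dosed harder than their nephrologist would choose.** The nephrologists' own PTH targets are not stated. The routine titration rule says only that increases depend on PTH and calcium, the explicit increase steps follow a calcium drop, and the over-suppression rule acts only below the KDIGO range. The width of one range against the other does not measure altered care.
- **That the labeling period, target or dosing will be kept from patients.** The study methods to be explained are summarised as "namely the assessment of physical exam and medical history; the evaluation by imaging modalities; the collection of blood; and bone biopsy will be described". This is a short list by category, and the consent form, which may say more, is not in the file. Silence in the list is not evidence of non-disclosure.
- **That the assurance that patients "will receive the same standard medical care regardless of participation will be emphasized" is a second false statement.** It is attached to the option not to take part and is naturally read as reassurance for those who decline.

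**Conclusion.** The point holds in a limited form. The planned statement is wrong as written, which is more than a missing detail: following it would give participants an inaccurate account of drug start in Aim 1 and of the PTH target and dosing guidance in all aims. The sentence ruling out any risk of altered management has the same fault.

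The weight is minor to moderate. The documented facts are an 18-day period before the first dose for 20 patients, and a 300-400 pg/mL target within a 160-720 pg/mL controlled range for 35. The effect on any patient's actual care is unknown, since neither usual start dates nor usual PTH targets are given. The conclusion concerns the consent plan in the protocol, not what patients were told. It assumes that the site's 720 pg/mL threshold applies and that the dosing section's target range is the one in the aim descriptions.

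**What to change.** In the Informed Consent section, replace the statement about management with:

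*We will explain that in Aim 1 etelcalcetide is not started until the initial 18-day labeling period is complete; that in all aims the study uses a PTH target of 300-400 pg/mL and the protocol's dosing guidance, which the treating physician has accepted; and that final treatment decisions stay with the nephrologist.*

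Reword the concluding sentence on risk to match, so that it no longer rules out any change in management. Then check that the consent form says the same.

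The cost is one wording amendment through the IRB and a comparison with the consent form. Visits, endpoints, dosing rules, sample size and analysis are unchanged.
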